12.4 Planned Final Analyses

Final analysis will take place 1 year after the last patient entered the study.

Sample size determinationThe trial will recruit 30 patients with the flexibility to recruit more if required. Given the rare nature of the disease bayesian probability plots for a binary outcome with an uninformative beta prior are used. Given these 30 patients, if the trial observed 11 responses there would be a 60% chance that the true response rate is greater than 35%. Given 13 responses are observed there would be an 84% chance that the true response rate is greater than 35%. See appendix 2 for plots for different scenarios.

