- Active autoimmune disease that might deteriorate when receiving an immunostimulatory agent. Patients with diabetes type I, vitiligo, psoriasis, hypo- or hyperthyroid disease not requiring immunosuppressive treatment are eligible
- Known prior severe hypersensitivity to investigational product or any component in its formulations, including known severe hypersensitivity reactions to monoclonal antibodies (NCI CTCAE v4.03 Grade ≥ 3)

- Persisting toxicity related to prior therapy of Grade >1 NCI-CTCAE v 4.03; however, alopecia and sensory neuropathy Grade ≤ 2 or other Grade ≤ 2 not constituting a safety risk based on investigator's judgment are acceptable
- Pregnancy or lactation
- Known alcohol or drug abuse
- Clinically significant (i.e., active) cardiovascular disease: cerebral vascular accident/stroke (< 6 months prior to registration), myocardial infarction (< 6 months prior to registration), unstable angina, congestive heart failure (\geq New York Heart Association Classification Class II), or serious cardiac arrhythmia requiring medication
- Other severe acute or chronic medical conditions including colitis, inflammatory bowel disease, pneumonitis, pulmonary fibrosis or psychiatric conditions including recent (within the past year) or active suicidal ideation or behaviour; or laboratory abnormalities that may increase the risk associated with study participation or study treatment administration or may interfere with the interpretation of study results and, in the judgment of the investigator, would make the patient inappropriate for entry into this study
- Vaccination within 4 weeks of the first dose of avelumab and while on trial is prohibited except for administration of inactivated vaccines (e.g. the flu vaccine)
- Active infection requiring systemic therapy
- Major surgery within 4 weeks of trial entry
- Patients and partners of childbearing potential not willing to use two methods of effective contraception during and for 60 days after therapy

Trial Duration

Patients will be recruited over 24 months from 13 Trials Acceleration Programme (TAP) and non-TAP centres.

Following registration, patients will receive 8 cycles (each of 28 days duration) of avelumab (each cycle being two, fortnightly infusions of the antibody) with the possibility of continued treatment if the patient is benefitting. The patient will have an end of treatment visit within 28 days of the end of the last cycle.

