3. TRIAL DESIGN

This is a single arm phase 2a trial to determine responses to avelumab in patients with refractory and relapsed PTCL. A single arm study has been selected to determine evidence of activity in PTCL to further evaluate in a larger trial. Patients will be recruited over a 24-month period and will receive 8 cycles of treatment with the possibility of continued treatment if the patient is showing clinical benefit. Patients will continue to be followed up for progression and survival for one year after the end of the trial treatment.

The trial will enrol 30 patients with the flexibility to enrol more, up to 35, if required. Based on 30 patients in the trial, if 11 responses were obtained this would give a probability of 60% that the response rate is greater than 35%. If 13/30 responses were obtained there is a probability of 84% that the response rate is greater than 35%. Other possible outcomes, both for 30 and 35 patients, have been plotted and are presented (Appendix 2).

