6. TRIAL ENTRY

Patients will be registered to the trial via the Cancer Research UK Clinical Trials Unit (CRCTU) by phone or using the CRCTU systems portal. An eligibility checklist and registration form (found in the ISF) should be completed prior to registration by the Investigator or designee.

Registration via CRCTU systems portal:

<https://www.cancertrials.bham.ac.uk/AvailTLive>

Login details will be provided by the trials office as part of site initiation. The patient trial number will be provided by the online system. A report can be printed as confirmation.

Registration via [contact]

9am-5pm Monday to Friday

The patient trial number will be given over the telephone, followed by a fax confirmation.

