7.3.5 Radiological Assessment – CT scans

A contrast enhanced CT scan of the neck, chest, abdomen and pelvis will be performed at cycles 3, 6 and 8 of treatment to assess response during treatment. If the patient discontinues treatment early an End of treatment scan should be performed, if a scan has not been conducted with the last 28 days. Scans should be reported with two dimensional measurements of each lesion in millimetres (mm) if measureable.

Immunotherapeutic agents such as avelumab may produce antitumor effects by potentiating endogenous cancer-specific immune responses. The response patterns seen with such an approach may extend beyond the typical time course of responses seen with cytotoxic agents, and can manifest as a clinical response after an initial increase (pseudo-progression) in disease burden. The Investigator's judgment of radiological response on early CT scans should be based on the overall benefit-risk assessment and the patient's clinical condition, including performance status, clinical symptoms, adverse events and laboratory data.

If the patient has not progressed after 8 cycles they will continue to be followed up with CT scans at 12, 16 and 20 months from treatment start or sooner if the investigator is concerned there may be disease progression. After 20 months from treatment start radiological follow-up will be as per local standard with data collected every 6 months.

Response will be assessed according to the Revised Response Criteria for malignant lymphoma²⁷ (appendix 1).

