7.9 Patient Follow Up

All patients will need to be followed up for safety (AEs) up to 30 days (+/- 5 days) after the last dose of avelumab and for disease progression / survival until the end of the trial (minimum of 12 months follow-up from the date of commencing treatment for the last patient).

If the patient stops trial treatment but has not progressed, they will be reviewed with a CT scan of neck, chest, abdomen and pelvis at 8, 12, 16 and 20 months or on clinical suspicion of progression (whichever is sooner).

If there is no evidence of progression after 20 months, patients will have no specific trial follow up, but their referring physician may be contacted every 6 months to determine progression and survival data.

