12.1.2 Secondary outcome measures

- Toxicity assessed using CTCAE v4.0 will be defined as the number and proportion of patients who experience one or more grade 3 or 4 adverse event or serious adverse event of any grade
- Best overall response (Partial Remission (PR) + Complete Response (CR)) at any time of treatment will be assessed using contrast-enhanced CT scans of the neck, chest, abdomen and pelvis, using the Revised Response Criteria for Malignant Lymphoma (²⁷)
- Maximum percentage change in the sum of the product of diameters (SPD) of target tumour masses assessed by contrast-enhanced CT scans of the neck, chest, abdomen and pelvis, using the Revised Response Criteria for Malignant Lymphoma²⁷
- Duration of response is defined as the time from first documented response until relapse/progression, as determined by the Revised Response Criteria²⁷, or death. Patients who are relapse/progression free and alive will be censored at date last seen.
- Progression free survival is defined as the time from date of registration to the date of disease progression or date of death from any cause. Patients not reaching progression or death at the time of analysis will be censored at the last date they were known to be alive and progression free. Patients will be followed up for a minimum of 12 months.
- Overall survival time is defined as the time from date of registration to the date of death from any cause. Patients discontinuing the study, lost to follow-up or still alive at the end of the study will be censored at the date of last follow-up. Patients will be followed up for a minimum of 12 months.

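### Follow-up length is set in non-equivalent ways, and the single planned final analysis leaves little or no margin for the last patient's 12-month scan

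*Combined protocol and SAP*

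**What the plan says.** All the places are in the combined protocol and SAP.

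- **Section 12.4** fixes the only planned final analysis: "Final analysis will take place 1 year after the last patient entered the study". It does not define entry. Section 6, Trial Entry, describes registration: "Patients will be registered to the trial via the Cancer Research UK Clinical Trials Unit (CRCTU) by phone".
- **Section 3**: "Patients will continue to be followed up for progression and survival for one year after the end of the trial treatment".
- **Section 7.9**: follow-up for progression and survival runs to the end of the trial, with a "minimum of 12 months follow-up from the date of commencing treatment for the last patient".
- **Section 12.1.2**, within both the PFS and OS definitions: "Patients will be followed up for a minimum of 12 months". That sentence names no origin, but the endpoint does: "Progression free survival is defined as the time from date of registration to the date of disease progression". OS also runs from registration.
- **Section 11** ends the trial at the last patient's last visit.
- **Section 7.3.5**, for patients who have not progressed after 8 cycles: "CT scans at 12, 16 and 20 months from treatment start or sooner".
- **Synopsis, Trial Duration**: "Following registration, patients will receive 8 cycles (each of 28 days duration) of avelumab". Treatment therefore starts after registration; no maximum interval is given.

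Section 12.2 promises Kaplan-Meier estimates at 6 and 12 months for time-to-event outcomes. Section 12.1.2 censors PFS with reference to the time of analysis and OS with reference to the end of the study.

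**The concern.** The follow-up statements use three different clocks (registration, treatment start, end of treatment), and the final analysis is tied to the earliest if entry means registration. The 12-month CT is tied to treatment start. For the last entrants, the scan that supports the 12-month disease assessment may not exist, or may not be reported, when the data are analysed. Duration of response is more exposed, because its clock starts only at first response and the plan schedules no later analysis to pick up the 16- and 20-month scans. The different reference dates for censoring PFS and OS add a further ambiguity: if the end of the study is the last 20-month visit, the two dates are months apart.

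**Working it through.** **Plan's own figure.** The only design calculation in section 12.4 is the posterior probability that the response rate exceeds 35%. A Beta(1,1) prior gives 60.3% for 11/30 (Beta(12, 20)) and 84.1% for 13/30 (Beta(14, 18)), matching the stated 60% and 84%. The timing point does not depend on it.

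**Inputs.**
- Treatment: 8 × 28 = 224 days. One month = 365.25/12 = 30.44 days, so 224 days = 7.36 months.
- Recruitment: 30 patients over 24 months (730.5 days). Uniform accrual is an assumption: 30/730.5 = 0.0411 patients per day.
- L, the lag from registration to first dose: not stated; assumed 0 to 28 days.
- Day 0 is the last patient's registration. With entry read as registration, the final analysis is at day 365.25.

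**Last patient at the final analysis.** Time from treatment start is 365.25 − L. The 12-month CT is due at 365.25 + L. Section 3 needs L + 224 + 365.25 days, so its shortfall is 224 + L.

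| L (days) | Months from treatment start | Shortfall against 7.9 and 12-month CT (days) | Shortfall against section 3, days (months) |
|---|---|---|---|
| 0 | 12.0 | 0 | 224 (7.4) |
| 7 | 11.8 | 7 | 231 (7.6) |
| 14 | 11.5 | 14 | 238 (7.8) |
| 28 | 11.1 | 28 | 252 (8.3) |

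If the ±3 day window of section 7.2 applies to follow-up scans (the documents do not say so), the CT falls between 3 days before and 3 days after the analysis date at L = 0, and 25 to 31 days after it at L = 28.

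**Patients affected.**
- 12-month CT: 0.0411 × 28 = 1.15 at most, so the last patient and 0 to 1 others.
- Section 3: 0.0411 × 224 = 9.2 to 0.0411 × 252 = 10.3, so about 9 to 10 of 30 lack a full year after 8 cycles. Fewer if patients stop early; more if they continue beyond 8 cycles.

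**12-month duration of response.** Scans follow the day 15 dose and precede the next cycle (Table 2 footnote). A patient first responding t days after treatment start, with L = 0, has 12 months of response observable only if registered at least t days before the last patient. The share of entrants cut off earlier is t/730.5:
- cycle 3 scan, days 70 to 84: 9.6% to 11.5%
- cycle 6 scan, days 154 to 168: 21.1% to 23.0%
- cycle 8 scan, days 210 to 224: 28.7% to 30.7%

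That is roughly 10% to 30%, depending on when response is first seen. A lag of 28 days adds 28/730.5 = 3.8 percentage points. With 11 responders (an illustrative count from section 12.4, response assumed unrelated to entry date), about 1 to 3 are affected.

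**What is not affected.** With L = 28 and an end-of-treatment visit 28 days after cycle 8, the last patient finishes at day 28 + 224 + 28 = 280, leaving 85 days before the final analysis. The primary endpoint is complete. OS runs from registration, and the last patient has 12.0 months, so the 12-month OS estimate is supported. The section 12.1.2 minimum, read from registration, is met exactly.

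**The case against.** The strongest reply is that section 12.4 times an analysis and does not end follow-up. Sections 7.9 and 11 let follow-up continue to the last visit, so the year after treatment and the later scans can still be collected. That is correct. What remains is that no planned analysis would use those data.

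A reader might infer that the protocol's 12-month minimum is simply not delivered. The documents do not support that. The shortfall exists only against section 7.9 and the CT schedule, only by the unstated lag, and only if entry means registration. If it means first dose, the dates coincide and what is left is the lack of time to perform and report the scan.

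A reader might also take the 10% to 30% shares, or the 17% (4/24) and 33% (8/24) of entrants not reaching the 16- and 20-month scans by the cut, as the result of mismatched origins. They are ordinary administrative censoring from staggered entry. Kaplan-Meier handles it, no 16- or 20-month estimate is planned, and delaying the cut by a few weeks barely changes the shares.

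The effect on 12-month PFS is also small. PFS runs from registration and the scan from treatment start, so with any appreciable lag a progression first seen on the 12-month CT is dated after the landmark for every patient. A missing scan in the last one or two patients can at most bring a censoring date forward.

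**Conclusion.** The inconsistency is real and should be corrected, but its consequences are limited. Sections 3, 7.9, 11, 12.1.2 and 12.4 do not define one follow-up period. The largest conflict is with section 3: about 19.4 months from treatment start for a patient completing 8 cycles, against a final analysis at least 224 days earlier for the last such patient. The conflict with section 7.9 and the 12-month CT is 0 to 28 days under the assumed lag, touching about 1 to 2 of 30 patients, and it depends on reading entry as registration.

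The cost is precision: marginal for PFS, and mainly for 12-month duration of response, where roughly 10% to 30% of entrants could not be observed long enough. These counts assume uniform 24-month accrual. It would be wrong to infer that the primary response endpoint or 12-month OS is compromised; neither is.

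**What to change.** 1. In section 12.4, define the origin and set the data cut after the last patient's 12-month CT, timed from treatment start, has been done and reported.
2. Reconcile sections 3, 7.9 and 12.1.2 to one follow-up length and one origin. Change 1 alone does not satisfy section 3, so the sponsor must decide openly whether its longer period stands.
3. Use one cut-off date for censoring PFS and OS.
4. Keep the end of trial in section 11 late enough for the 16- and 20-month scans. Moving it to the 12-month date would cut off scans that the protocol already schedules.
5. Plan an updated analysis of duration of response and PFS once those scans are complete. A patient first responding as late as the end of cycle 8 would then have 20 − 7.4 = 12.6 months from first response, so the 12-month duration estimate would no longer be limited by the cut. The 20-month point also lies beyond the 19.4 months that section 3 implies for 8 cycles.

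The cost is a final analysis a few weeks later, one further descriptive update, and changes of wording. No additional scans are needed.

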13. TRIAL ORGANISATIONAL STRUCTURE

13.1 Sponsor

The trial is sponsored by the University of Birmingham.

13.2 Coordinating Centre

The trial is being conducted under the auspices of the Cancer Research UK Clinical Trials Unit (CRCTU), University of Birmingham according to their local procedures.

13.3 Trial Management Group

A TMG will be established and will include the Chief Investigator, co-investigators, the trial statistician and trial coordinators. Key trial personnel will be invited to join the TMG as appropriate to ensure representation from a range of professional groups. Notwithstanding the legal obligations of the Sponsor and Chief Investigator, the TMG will be responsible for the day-to-day running and management of the trial and will meet by teleconference or in-person as required, at least every 6 months during the trial treatment period.

13.4 Trial Safety Committee

A TSC, with an independent chair, will provide overall supervision for the trial and provide advice through its independent chair. The ultimate decision for the continuation of the trial lies with the TSC. The TSC will meet at least 6 months after the first patient has been recruited and every 6 months thereafter during the recruitment and treatment period, to monitor all safety, futility and primary activity data.

13.5 Finance

This is an Investigator-initiated and Investigator -led trial funded by the Bloodwise Trials Acceleration Programme (TAP) and Pfizer.

Payments will be made to NHS Trusts for research costs associated with the trial. No other individual per patient payment will be made to NHS Trusts, Investigators or patients.

This trial is also included in the NIHR CRN portfolio.

This project is supported by the facilities funded through Birmingham Science City: Translational Medicine Clinical Research Infrastructure and Trials Platform, an Advantage West Midlands (AWM) funded project which forms part of the Science City University of Warwick and University of Birmingham Research Alliance.

14. ETHICAL CONSIDERATIONS

The trial will be performed in accordance with the recommendations guiding physicians in biomedical research involving human subjects, adopted by the 18th World Medical Association General Assembly, Helsinki, Finland, June 1964, amended at the 48th World Medical Association General Assembly, Somerset West, Republic of South Africa, October 1996 (website: <http://www.wma.net/en/30publications/10policies/b3/index.html>).

The trial will be conducted in accordance with the Research Governance Framework for Health and Social Care, the applicable UK Statutory Instruments, (which include the Medicines for Human Use Clinical Trials 2004 and subsequent amendments and the General Data Protection Regulation and the Data Protection Act (2018) and Human Tissue Act 2008) and Good Clinical Practice (GCP). This trial will be carried out under a Clinical Trial Authorisation in accordance with the Medicines for Human Use Clinical Trials regulations. The protocol will be submitted to and approved by the main Research Ethics Committee (REC) prior to circulation.

Before any patients are enrolled into the trial, the Principal Investigator at each site is required to obtain local R&D approval. Sites will not be permitted to enrol patients until written confirmation of R&D approval is received by the Trials Office.

It is the responsibility of the Principal Investigator to ensure that all subsequent amendments gain the necessary local approval. This does not affect the individual clinicians' responsibility to take immediate action if thought necessary to protect the health and interest of individual patients.

15. CONFIDENTIALITY AND DATA PROTECTION

Personal data recorded on all documents will be regarded as strictly confidential and will be handled and stored in accordance with the General Data Protection Regulation and the Data Protection Act (2018). With the patient's consent, their initials and date of birth will be collected at trial entry. Patients

will be identified using only their unique trial number, initials and date of birth on the Case Report Form and correspondence between the Trials Office and the participating site. However patients are asked to give permission for the Trials Office to be sent a copy of their signed Informed Consent Form which will not be anonymised. This will be used to perform in-house monitoring of the consent process.

The Investigator must maintain documents not for submission to the Trials Office (e.g. Patient Identification Logs) in strict confidence. In the case of specific issues and/or queries from the regulatory authorities, it will be necessary to have access to the complete trial records, provided that patient confidentiality is protected.

The Trials Office will maintain the confidentiality of all patient's data and will not disclose information by which patients may be identified to any third party other than those directly involved in the treatment of the patient. Representatives of the AVAIL-T trial team may be required to have access to patient's notes for quality assurance purposes but patients should be reassured that their confidentiality will be respected at all times.

16. INSURANCE AND INDEMNITY

University of Birmingham employees are indemnified by the University insurers for negligent and non-negligent harm caused by the design or co-ordination of the clinical trials they undertake whilst in the University's employment.

In terms of liability at a site, NHS Trust and non-Trust hospitals have a duty to care for patients treated, whether or not the patient is taking part in a clinical trial. Compensation is therefore available via NHS indemnity in the event of clinical negligence having been proven.

The University of Birmingham is independent of any pharmaceutical company, and as such it is not covered by the Association of the British Pharmaceutical Industry (ABPI) guidelines for patient compensation.

17. PUBLICATION POLICY

Results of this trial will be submitted for publication in a peer reviewed journal in accordance with the TAP publication policy. The manuscript will be prepared by the Trial Management Group (TMG) and authorship will be determined in line with the TAP publication policy.

Any secondary publications and presentations prepared by Investigators must be reviewed by the TMG. Manuscripts must be submitted to the TMG in a timely fashion and in advance of being submitted for publication, to allow time for review and resolution of any outstanding issues. Authors must acknowledge that the trial was performed with the support of The University of Birmingham and Bloodwise. Intellectual property rights will be addressed in the Clinical Study Site Agreement between Sponsor and site.

